5.2 Sample Size and Estimated Duration of Study

A total of 80 subjects will be vaccinated with either Pfs230D1-EPA/Matrix-M (n=60) or the rabies vaccine comparator (n=20). The last study visit will occur at Month 14 (12 months after the final immunization). Up to 150 subjects will be screened to accommodate possible screening failures.

The sample size was derived to be able to demonstrate safety, tolerability, and immunogenicity of the study vaccine as described in Section 14.1.

5.3 Study Definitions

Screened: Subjects will receive a screening identification number when the informed consent is signed, and will either be determined as "enrolled" or "screen failures" as noted below.

- Screening may be completed over the course of multiple visits.
- Screening will occur within 56 days prior to enrollment into the study.
- If screening laboratories are obtained >56 days prior to planned enrollment (Day -7), then the subject will need to have a repeat physical exam, medical history review and all laboratories outside of the window will need to be collected again (inclusive of safety labs, human immunodeficiency virus [HIV],) to confirm whether the subject may proceed to enrollment

Enrolled: Subjects will be considered enrolled beginning on Day -7, and the final study number will be assigned at this point.

Randomized: Participants will be randomized to one of the study groups. See Section 14.5 for details.

Screen Failures: Subjects are considered screen failures when they meet 1 of the following criteria after signing consent:

- Screening results reveal that the subject is ineligible per Section 8.1
- Subject withdraws consent before Day -7 (i.e., enrollment).

Withdrawn: Participants will be considered to be withdrawn from the study if they meet any of the withdrawal criteria in Section 12.11 prior to completing the final study visit.

Completed: Subjects are considered completed when they complete the final study visit for their arm.

Lost to follow-up: A participant will be considered lost to follow-up if he or she fails to attend a required study visit and cannot be located. Study site staff will make at least 3 attempts to contact participants to complete the remaining study visits. These contact attempts should be documented in the participant's study file. Should the participant continue to be unreachable, they will be considered to have withdrawn from the study with a primary reason of lost to follow-up.

6 Study Population

6.2 Recruitment Plan

Community permission will be obtained from village elders and other community members in Sotuba after explanation and discussion of the study at a community meeting. A general announcement about the study will be made at the time of community permission, using local radio or any traditional channel of communication. The announcement will include general information about the study as well as contact information for the study site/staff for those interested in participating.

6.3 Inclusion Criteria

All of the following criteria must be fulfilled for a volunteer to participate in this trial:

- 1. Age: \geq 18 years old and \leq 50 years old.
- 2. Available for the duration of the trial.
- 3. Known resident or long-term resident (more than 1 year) of Sotuba, Mali or surrounding villages.
- 4. Able to provide proof of identity to the satisfaction of the study clinician completing the enrollment process.
- 5. In good general health and without clinically significant medical history in the opinion of the investigator.

- 6. Females of childbearing potential must be willing to use reliable contraception from 21 days prior to Study Day 0 and until 1 month after the last vaccination.
 - A reliable method of birth control includes **one** of the following:
 - o Confirmed pharmacologic contraceptives (parenteral) delivery.
 - o Intrauterine or implantable device.
 - EXCEPTIONS to required pregnancy prevention includes the following:
 - o Postmenopausal state: defined as no menses for 12 months without an alternative medical cause.
 - o Surgical sterilization.
- 7. Willing to have blood samples stored for future research.

6.4 Exclusion Criteria

An individual will be excluded from participating in this trial if any one of the following criteria is fulfilled:

- 1. Pregnant, as determined by a positive urine or serum beta human choriogonadotropin (β-hCG) test (*if female*).
 - NOTE: Pregnancy is also a criterion for discontinuation of any further vaccine dosing.
- 2. Behavioral, cognitive, or psychiatric disease that in the opinion of the investigator affects the ability of the subject to understand and comply with the study protocol at a level appropriate for the subject's age.
- 3. Hemoglobin, white blood cell (WBC), absolute neutrophil count, or platelet levels outside the local laboratory-defined limits of normal. (Subjects may be included at the investigator's discretion for "not clinically significant" values outside of normal range and ≤ Grade 2.)
- 4. Alanine transaminase (ALT) or creatinine (Cr) level above the local laboratory-defined upper limit of normal. (Subjects may be included at the investigator's discretion for "not clinically significant" values outside of normal range and ≤ Grade 2.)
- 5. Infected with HIV.
- 6. Evidence of clinically significant neurologic, cardiac, pulmonary, hepatic, endocrine, rheumatologic, autoimmune, hematological, oncologic, or renal disease by history, physical examination, and/or laboratory studies.
- 7. History of receiving any investigational product within the past 30 days.
- 8. Current or planned participation in an investigational vaccine study until the time period of the last required study visit under this protocol.
- 9. Medical, occupational, or family problems as a result of alcohol or illicit drug use during the past 12 months.
- 10. History of a severe allergic reaction or anaphylaxis.

11. Known:

- Severe asthma, defined as asthma that is unstable or required emergent care, urgent care, hospitalization, or intubation during the past 2 years, or that has required the use of oral or parenteral corticosteroids at any time during the past 2 years.
- Autoimmune or antibody-mediated disease including but not limited to: systemic lupus erythematosus, rheumatoid arthritis, multiple sclerosis, Sjögren's syndrome, or autoimmune thrombocytopenia.
- Immunodeficiency syndrome.
- Seizure disorder (exception: history of simple febrile seizures).
- Asplenia or functional asplenia.
- Use of chronic (≥14 days) oral or intravenous (IV) corticosteroids (excluding topical or nasal) at immunosuppressive doses (i.e., prednisone >10 mg/day) or immunosuppressive drugs within 30 days of Study Day 0.
- Allergy to latex or neomycin.

12. Receipt of:

- Live vaccine within 4 weeks prior to enrollment or a killed vaccine within 2 weeks prior to enrollment.
- Immunoglobulins and/or blood products within the past 6 months.
- Investigational malaria vaccine in the last 2 years.
- 13. Any other condition that in the opinion of the investigator would jeopardize the safety or rights of a subject participating in the trial, interfere with the evaluation of the study objectives, or would render the subject unable to comply with the protocol.

Co-enrollment guidelines: Co-enrollment in other trials is limited. Consideration for co-enrollment in trials evaluating the use of a licensed medication will require the approval of the PI. Study staff should be notified of co-enrollment on any other protocol as it may require the approval of the investigator. Enrolled subjects will be informed that they may be invited to participate in other subsequent studies.

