Verorab Rabies Vaccine: One dose consists of the administration of 0.5 mL of vaccine via the intramuscular route and contains

rabies virus, WISTAR Rabies PM/WI38 1503-3M strain

 $(inactivated) \ge 2.5 \text{ IU}.$

Subject Sample Size: N=80 (n=60 Pfs230D1-EPA/Matrix-M; n=20 rabies control)

Accrual Ceiling: N=150

Accrual Period: September 2021-October 2021

Study Duration: Start Date: approximately September 2021

End Date: approximately June2023 (includes data analysis)

Study participants will be enrolled for a total of approximately 14 to 16 months depending upon timing of screening

Study Population:

Healthy male and female adults (18 to 50 years of age) who reside in Sotuba and surrounding villages, Mali

Study Design:

This is a Phase 1, dose-escalating, randomized, double-blind, comparator-controlled study to assess the safety, tolerability, immunogenicity and transmission-blocking activity (TBA) of a 3-dose regimen of Pfs230D1-EPA/Matrix-M versus rabies vaccine in healthy adults. This will be a first-in-human assessment of Pfs230D1-EPA/Matrix-M. Participants will be randomized to one of the study arms. Participants will be followed for 12 months from the last dose of study vaccine for safety and tolerability, as well as immunogenicity and functional antibody responses.

The study groups and arms are as follows. For all participants, the assigned study vaccine will be administered at Days 1, 29, and 57.

Group 1: Pilot Group

- **Arm 1a** (n=5): 12.5 μg Pfs230D1-EPA/25 μg Matrix-M
- **Arm 1b** (n=5): 20 μg Pfs230D1-EPA/50 μg Matrix-M
- **Arm 1c** (n=5): 40 μg Pfs230D1-EPA/50 μg Matrix-M
- Arm 1d (n=4): rabies vaccine (standard dose)

Group 2: Main Group

- Arm 2a (n=15): 12.5 μg Pfs230D1-EPA/25 μg Matrix-M
- Arm 2b (n=15): 20 μg Pfs230D1-EPA/50 μg Matrix-M
- Arm 2c (n=15): 40 μg Pfs230D1-EPA/50 μg Matrix-M
- Arm 2d (n=16): rabies vaccine (standard dose)

Study Objectives:

Primary Objective:

• To assess in African adults the safety and the reactogenicity of administration of Pfs230D1-EPA/Matrix-M (first-in-human) as compared to the rabies vaccine control

Secondary Objectives:

- To assess level of and duration of humoral immune responses as measured by enzyme-linked immunosorbent assay (ELISA) titer response to Pfs230D1M after third immunization
- To assess the functional antibody response by standard membrane feeding assay (SMFA) to Pfs230D1M

Exploratory Objectives:

- To explore cellular and humoral responses to Pfs230D1M

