3.2 Pfs230D1M-EPA/AS01 in Healthy Malian Adults (#17-I-N006)

The double-blind, comparator-controlled, Phase 1 trial of Pfs230D1M-EPA/AS01 in Malian adults (NIAID protocol #17-I-N006) evaluated Pfs230D1M-EPA/AS01 at escalating doses of 13 µg and 40 µg administered on a schedule of 0, 1, and 6 months in a pilot study.

In summary, preliminary ELISA and SMFA results suggested that the two doses induced similar activity. In the main phase of the study, the 40- μg dosage was used for vaccination. Unblinding of a larger cohort of this trial, with 60 subjects in the full-dose arm (3 doses of 40 μg at 0, 1, and

6 months) and 60 subjects in a fractional-dosing arm (2 vaccinations at 0 and 1 month of 40 μ g Pfs230D1M/AS01 and third vaccination at 6 months of 1/5 of the full dose), occurred in March of 2018. The results of the trial established the full 3-dose regimen using 40-ug dosage as the benchmark for future trials, and demonstrated safety and tolerability of the regimen. A booster dose of Pfs230D1M (40 μ g) was administered approximately 12 months after the third immunization.

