3.2.1 Safety of Pfs230D1M-EPA/AS01 in Healthy Adults

Pilot Phase

In the pilot phase of the study, there was a staggered dose escalation of Pfs230D1M and Pfs25M, given individually and in combination. In the Pfs230D1M arms alone, vaccinations with the low dose of Pfs230D1M (13 μ g) and high dose of Pfs230D1M (40 μ g) were overall well-tolerated. Most of the related AEs were mild (Grade 1; 13 μ g: 23/29, 79%; 40 μ g: 42/51, 82%), with the majority being injection site pain. Laboratory abnormalities were also observed, with the majority being transient, asymptomatic Grade 1 (mild) and Grade 2 (moderate) neutropenias. As the high dose (40 μ g) of the Pfs230D1M/AS01 was determined safe and tolerable in the pilot study, it was selected to be used for the main phase of the study.

Main Phase

In the main phase of the trial, there was a full-dose arm (n=56) and a fractional-dose arm (n=61). The full-dose arm received Pfs230D1M-EPA/AS01 at 40 μg at 0, 1, 6, and 18 months. The fractional-dose arm received Pfs230D1M-EPA/AS01 at 40 μg at 0, 1, and 18 months and received a fractional dose of 8 μg of Pfs230D1M-EPA/AS01 at dose #3 at 6 months. Because there is no fractional dosing in the proposed trial, full details of the fractional dosing arm are not provided here; overall, the AE profile was similar to that of the full-dose arm, and further details can be found in the Investigator Brochure.

First 3 vaccinations: In the full-dose arm (n=56), the first three vaccinations were well tolerated with 66% (252/383) of the total AEs being mild. The most common Grade 1 AEs were injection site pain (95/252; 38%) followed by headache and malaria. Of the related Grade 2 AEs, 16/24 (67%) were injection site pain. Other related Grade 2 AEs were 2 episodes each of fever, headache, arthralgias, and neutropenia. Grade 1 injection site pain was reported in the full-dose arm in 95/168 (57%) doses, fractional-dose arm in 78/180 (43%) doses and control arm in 39/360 (11%) doses. Grade 2 injection site pain was also significantly greater in the full-dose and fractional-dose arms compared to the control. Grade 1 headaches were significantly greater in the full-dose arm than the control arm.

Booster dose: The fourth dose of Pfs230D1M-EPA/AS01 was well tolerated; most AEs were mild (Grade 1 AEs; 160/363, 44%). The most commonly reported Grade 1 AE was injection site

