pain, which was observed in about half of Pfs230D1M vaccinees. Of the related Grade 2 AEs, injection site pain was most common (7/11, 63%) followed by headache, fatigue, and injection site movement impairment in one subject. There were no related Grade 3 AEs. Participants in the Pfs230D1M booster arm experienced significantly more Grade 1 injection site pain and headache than the comparator arm. Grade 2 injection site pain was also reported more frequently in the Pfs230D1M arm but was not significantly different from the comparator.

[figure not shown]
3.2.2 Immunogenicity and Functional Activity (SMFA) of Pfs230D1M-EPA/AS01 in Healthy Adults (Primary Series + 4th Dose; Year 1 + 2)

Vaccination induced detectable antibody titers 2 weeks after the first dose, which increased further after dose 2, but the peak after a third dose was not significantly higher (Figure 11). There were no differences in titers between the low and high vaccine doses. Antibody function was assessed 2 weeks and 12 weeks after dose 2 (Figure 12). Anti-Pfs230 was sufficient to induce 100% TRA 2 weeks post dose 2, which was still >90% 12 weeks post dose 2. In contrast, anti-Pfs25 did not exceed 80% TRA post dose 2. The combination of Pfs25 and Pfs230 was not superior to Pfs230 alone for inducing functional serum activity.

Figure 11. Antibody Responses to Pfs230D1M-EPA/AS01 after Low Dose and High Dose Vaccinations of Adults in Sotuba, Mali during Pilot Phase trial.

[figure not shown]
A Low Dose Groups

B High Dose Groups

Response assessed by enzyme-linked immunosorbent assay (ELISA). (A) shows antibody responses of Malian adults after administration of low-dose vaccinations of Pfs230D1M-EPA/AS01 (either 13 μg Pfs230D1M alone or 16 μg Pfs230D1M-EPA/AS01 plus Pfs25M) at various time points out to 6 months. (B) shows antibody responses after administration of high-dose vaccinations of Pfs230D1M-EPA/AS01 (either 40 μg Pfs230D1M alone or 47 μg Pfs230D1M-EPA/AS01 plus Pfs25M) at various timepoints out to 6 months. Red arrows indicate immunization administrations at 0, 1, and 6 months. Dotted lines represent antibody titers to Alhydrogel-adjuvanted Pfs230D1M-EPA obtained in previous studies.

Figure 12. Antibody Function by Standard Membrane Feeding Assay to Pfs230D1M-EPA/AS01 after Low-Dose and High-Dose Vaccinations of Adults in Sotuba, Mali during Pilot Phase trial.

[figure not shown]

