3.2.3 Functional Activity by Direct Skin Feeds

Direct skin feeds (DSFs) were also used to assess vaccine activity. During the rainy season in 2017 (Year 1, main phase) and 2018 (Year 2, fourth dose), a total of 4861 DSFs were performed in 2017 and another 5065 DSFs were completed in 2018. There were a total of 40 positive DSFs (0.82%) from 19 unique individuals in 2017; and a total of 88 positive DSFs (1.74%) from 25 unique individuals in 2018 (Table 4). A trend of lower infections in the full-dose regimen was observed in 2017 but was not significant. Positive DSFs were significantly less frequent in the full-dose regimen in 2018, a first and extremely important achievement in the field of malaria TBVs – in vivo functional activity.

0.41%

0.39%

0.006

0.006

N. DSF Positive N. feeds performed Group % Positive Comparator 76 4960 1.53% 2017 21 2462 0.85% 2018^ 55 2498 2.20% Pfs230/AS01 fractional dose 42 2450 1.71% 2017 14 1168 1.20% 2018* 28 1282 2.18% Pfs230/AS01 full dose 10 2516 0.40%

1231

1285

0.9423

0.8913

Table 4. Summary of DSF Results.

Twice weekly feeds for 12 weeks in 2017 and for 16 weeks in 2018. *, ^ proportion of infection between groups were significantly different by chi-square test.

5

5

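### Exclusion 12's two-year look-back leaves Sotuba adults who received Pfs230D1M-EPA/AS01 in the earlier pilot eligible for this trial of the same conjugate

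*Combined protocol and SAP*

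**What the plan says.** Section 6.4, exclusion 12, sets the look-back for earlier vaccine trials: "Investigational malaria vaccine in the last 2 years". The Protocol Synopsis gives "Accrual Period: September 2021-October 2021" and describes the population as healthy adults aged 18 to 50 "who reside in Sotuba and surrounding villages, Mali". Section 6.3 requires residence in that same area.

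The captions of Figures 11 and 12 (Section 3.2.2) show where the earlier AS01 pilot took place: responses were measured "after Low Dose and High Dose Vaccinations of Adults in Sotuba, Mali during Pilot Phase trial". Section 3.2 says the pilot vaccine was "administered on a schedule of 0, 1, and 6 months in a pilot study". Section 3.2.1 says of the 40 µg dose, on the strength of the pilot, that "it was selected to be used for the main phase of the study". Section 3.2.3 dates the main-phase skin feeds to the 2017 rainy season and the fourth-dose year to 2018.

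Other provisions that might apply:

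- Exclusion 7 covers any investigational product, but only for 30 days.
- Exclusion 8 covers current or planned vaccine studies.
- Exclusion 13 lets the investigator refuse someone whose condition would compromise assessment of the objectives. It is a matter of opinion and does not mention earlier vaccination.
- The screening list in Section 8.1 does not name earlier trial vaccination.
- Appendix A draws blood for ELISA on Day -7 and Day 1, but no titre limit governs entry.
- Section 14.5.1 describes no stratification by earlier vaccination. Sections 14.3.1 and 14.3.2 compare groups by Wilcoxon-Mann-Whitney with no stated baseline adjustment. The within-arm signed-rank test does use change from baseline.

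**The concern.** The trial is first-in-human for the Matrix-M formulation, but the antigen and carrier are those already given to Sotuba adults with AS01. A former pilot participant who enrols may carry residual anti-Pfs230 antibody or immune memory. In a vaccine arm, a recall response would be counted as the response to three doses of the new formulation. In the rabies arm, residual titre would raise the control values.

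The results exposed are antibody level and duration (a secondary objective), the dose-sparing question behind the 20 µg arm (Sections 1.2 and 1.2.1), and the ELISA results two weeks after the final dose, which Section 1.2 says will be reviewed before the Antigen Combination Trial begins. With 20 people per dose, chance allocation cannot be relied on to spread a few primed people evenly.

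**Working it through.** **1. Dates.** Accrual start minus look-back: September 2021 − 2 years = September 2019. For the end of accrual: October 2019. The pilot set the main-phase dose, and the main-phase feeds were in 2017, so the pilot series falls before or around 2017, roughly 4 years before accrual. That date is inferred, not printed. The conclusion does not depend on it closely: even a dose in late December 2018 is about 2 years 8 months before September 2021, outside the look-back.

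**2. Overlap.** Same village, adults in both trials, same Pfs230D1M-EPA conjugate. Section 6.1 gives Sotuba about 7,500 inhabitants, a resident research clinic and a long record of malaria vaccine trials. None of exclusions 7, 8 and 13 makes refusal mandatory for a recipient from about 2017.

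**3. Evidence of recall.** Section 3.2.2 reports higher Pfs230 responses after dose 4 than after dose 3. Section 3.2 puts dose 4 about 12 months after dose 3. No fold size is given, and nothing is reported at 4 years.

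**4. The plan's own power figures (Section 14.3.1).** Inputs: log ELISA mean 3.688, SD 0.549 at baseline; mean 5.357, SD 0.887 three months after dose 2. The ratio is exp(5.357 − 3.688) ≈ 5.3 (printed as 5.31). Simulated Wilcoxon-Mann-Whitney power, 20 versus 20:

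- Baseline versus post-dose 2: 1.00 (plan: over 0.99).
- 2.3-fold at alpha 0.05: 0.92 (plan: greater than 80%).

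Both agree with the plan.

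**5. Sensitivity, with assumed numbers of primed people.** Vaccine versus control, 20 versus 20, at the Bonferroni alpha 0.05/3 of Section 14.1. Primed controls are assumed to sit 0.5 to 1.67 natural-log units above baseline.

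| Primed controls of 20 | Power, true 2.3-fold | Power, true 5.3-fold |
|---|---|---|
| 0 | 0.80-0.82 | 1.00 |
| 2 | 0.57-0.73 | 1.00 |
| 4 | 0.28-0.65 | 0.99-1.00 |

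Dose versus dose with no true difference, nominal alpha 0.05, primed responses assumed 1 to 1.67 log units higher. Section 14 lists no formal test between doses, so this stands for the comparison that the dose-sparing aim implies.

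| Primed, one arm vs the other | False-positive rate |
|---|---|
| 0 vs 0 | 0.04-0.05 |
| 2 vs 0 | 0.06 |
| 4 vs 0 | 0.09-0.12 |
| 6 vs 0 | 0.13-0.22 |

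**6. Chance imbalance.** Allocating primed people at random to four groups of 20, the probability that some two groups differ by 3 or more is about 0.39 if 5 of the 80 are primed and 0.68 if 10 are.

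**7. Pilot arms.** One primed person is 1/5 = 20% of a pilot vaccine arm and 1/4 = 25% of the pilot rabies arm. Section 14.1 pools pilot and main arms, so this bears on pilot results shown alone.

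**The case against.** The strongest reply is that the effect may be negligible. The pilot's size is not printed, and some of its participants received Pfs25 alone or the comparator. If there were 40 Pfs230 recipients (an assumption), a random draw of 80 from 7,500 residents would contain 80 × 40/7,500 ≈ 0.43 of them. Volunteers are not a random draw, and 7,500 counts all ages, but the documents give no re-enrolment rate. One or two primed people in an arm barely move a rank test, and primed controls bias towards the null. Participants with residual titre would show it at Day -7 or Day 1, the signed-rank test uses change from baseline, and exclusion 13 permits refusal.

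Most of this stands as a limit on size. It does not close the gap. A baseline draw that is neither an entry test nor an adjustment variable removes nobody, change from baseline does not remove a recall response, and exclusion 13 obliges no one to refuse.

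Stronger readings that a reader might draw, and why the documents do not support them:

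- *A quantified shift in the arm mean.* Treating a primed person as 5.3-fold above arm peers gives exp(1.668 × k/20) = 1.09, 1.18 and 1.28 for k = 1, 2, 3. The arithmetic is right, but 5.3 is the post-dose-2 to baseline ratio, not the excess of a primed person over vaccinated peers. Section 3.2.2 found no significant rise in titre from dose 2 to dose 3 (p = 0.20 full dose, >0.99 fractional). Even taken at face value, the first two shifts lie within one standard error (0.887/√20 = 0.198; 0.42 and 0.84 SE).
- *Distorted reactogenicity.* Grade 1 injection-site pain followed 57% of the first three full doses, and about half of vaccinees reported it after dose 4, with no related Grade 3 events (Sections 3.2.1 and 3.2.2). With Alhydrogel it did not become more frequent on repeat dosing (Section 3.1.1).
- *Contamination of a naive population.* Malaria-exposed adults can have natural anti-Pfs230 antibody (Section 1.1), and a few Malian adults did at baseline (Section 3.1.2).

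**Conclusion.** The eligibility gap is real: a two-year look-back admits Sotuba adults vaccinated with this conjugate about 4 years earlier, and only a discretionary criterion could keep them out. The threat is to antibody level, duration and dose-sparing comparisons, chiefly for small effects and in the 5-person pilot arms. It does not extend to a vaccine-versus-control ELISA signal of the size seen with AS01, for which power stays at 0.99 or more even with 4 of 20 controls primed.

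The size cannot be fixed from the documents. It rests on three unknowns: how many Pfs230 recipients would re-enrol, whether priming or residual titre lasts about 4 years (a further response is documented only at about 12 months), and the pilot's actual dates. The simulated losses are conditional illustrations, not estimates. This is a cheap improvement worth making, not a flaw that invalidates the trial.

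**What to change.** Add to exclusion 12: *ever received a Pfs230-containing investigational vaccine*, checked at screening against the site's earlier trial records. Keep the two-year limit for other malaria vaccines. A lifetime bar on every EPA conjugate is not needed; the argument concerns Pfs230 priming.

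If the sponsor prefers to keep such volunteers, record prior Pfs230 receipt at screening and prespecify a sensitivity analysis of ELISA and SMFA that excludes them or adjusts for baseline titre.

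The cost is one eligibility line, a records check and a few ineligible volunteers, against a screening allowance of up to 150 for 80 places (Section 5.2). The sample size need not change.
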